### V. Distalization efficacy with respect to the third molar presence

Kinzinger et al (2004), evaluated the efficiency of a pendulum appliance for molar distalization related to second and third molar eruption stage. The studied sample included 36 adolescent patients in various stages of the molar dentition. The patients were divided into 3 groups (PG 1-3) according to the stage of eruption of their second and third molars. In PG 1 (18 patients), eruption of the second molars had either not yet taken place or was not complete. In PG 2 (15 patients), the second molars had already developed as far as the occlusal plane, with the third molars at the budding stage. In PG 3 (3 patients), germectomy of the wisdom teeth had been carried out, and the first and second molars on both sides had completely erupted. A modified pendulum appliance, including a distal screw and special preactivated pendulum springs was used for bilateral maxillary molar distalization. The study showed that the degree of tipping of maxillary second molar was greater when a third molar bud was in the direction of movement. Moreover, the study concluded that third molar bud could sometimes act as a fulcrum, affecting the efficiency of upper 1st molar distalization. After previously completed germectomy of the wisdom teeth, almost exclusively bodily distalization of both molars is possible. In the presence of both 2nd and 3rd molars the duration of distalization will be longer, greater forces will have to be applied, and more anchorage will be lost. This study recommended germectomy of wisdom teeth prior to ditalization.

Flores-Mir et al (2013), conducted a systematic review to evaluate the efficiency of molar distalization associated with the second and third molar eruption stage. A systematic computerized database search was done using several databases and out of the thirteen initially identified articles, only four fulfilled their final selection criteria. The results showed that three of the four studies showed no statistical significance in the linear amount of maxillary first molar distalization

based on the eruptive stage of the second and/or third molars, while the last study showed that the amount of distal movement of the first molars was significantly greater in the group with unerupted second molars. The study also noted that tipping of the first molar was greater when a third molar bud was located in the direction of movement. As a result, they concluded that effect of maxillary second and third molar eruption stage on both linear and angular maxillary molar distalization appears to be minimal. But this conclusion was based only on low–level of evidence clinical trials.

Jin Lee et al (2019), evaluated changes in the position of maxillary third molars with cone-beam computed tomography images in adolescents after total arch distalization using a modified C-palatal plate (MCPP) and to compare them with the changes in a matched control group. Forty adolescent patients (mean age, 12.6 years) were divided into MCPP and control groups. Cone-beam computed tomography images were taken before and after molar distalization (mean duration, 14.4 months) in the MCPP group and in the control group (mean duration, 12.9 months). The changes in the position, angulation, and rotation of the third molars were assessed, and the volumes of maxillary tuberosity were measured. The results showed that after distalization, the third molars moved backward (1.2 mm) and upward (0.5 mm) in the MCPP group with a significant difference (P < 0.003), and they moved downward and forward in the control group. The changes in rotation and angulation were insignificant. The volumes of maxillary tuberosity increased in both groups. The study concluded that maxillary total arch distalization caused unerupted third molars to move backward and upward, with an insignificant difference in the posttreatment volume of maxillary tuberosity. Therefore, it may be possible to perform maxillary total arch distalization in adolescents with unerupted third molars without a germectomy, at least in the short term.

# Database research:

A search was performed on electronic databases (PubMed, Cochrane library).

# Aim of the study

# **A-PICO format:**

# **Population:**

Adolescent patients having Class II molar relation with full permenant dentition including unerupted third molar. And indicated fore maxillary molar Distalization.

# Intervention:

Distalization of maxillary first molars using infra-zygomatic gear distalizer after extraction of maxillary third molars.

# **Comparator:**

Distalization of maxillary first molars using infra-zygomatic mini-implants as anchorage unit without extraction of maxillary third molars.

# **Outcome measure(s):**

	Outcome name	Measuring device	Measuring unit
Primary outcome	The total anteroposterior distance moved by the maxillary first molars.	Digital models using 3- shape scanner and program.	mm

		CBCT images using Anatomage software.	mm
Secondary outcomes	1-Maxillary first molar distalization rate.	Digital models using 3 shape scanner and program.	mm/month
	2-Maxillary first molar rotation	Digital models using 3 shape scanner and program.	Degree
	3- Intermolar width	Digital models using 3 shape scanner and program.	mm
	4-Maxillary first molar tipping and torque	CBCT images using Anatomage software.	Degree
	5-Maxillary first molar vertical changes	CBCT images using Anatomage software	mm

	6- Total anteroposterior distance moved by maxillary first and second premolars.	Digital models using 3 shape scanner and program.	mm
	7- Maxillary second molar tipping.	CBCT images using Anatomage software	Degree
	8-Maxillary third molar tipping	CBCT images using Anatomage software	Degree
	9-Maxillary third molar vertical changes	CBCT images using Anatomage software	mm
	10-Maxillary four incisors anteroposterior and vertical linear measurements.	CBCT images using Anatomage software	mm
	11- Maxillary four incisors torque.	CBCT images using Anatomage software	mm

# **B-Research question:**

Does extraction of the upper third molars have a different impact than nonextraction on distalizing maxillary first molars in Class II adolescents?

### **Objectives of the study research**

### **Research hypothesis:**

The null hypothesis was that the presence and extraction of unerupted maxillary third molars would have a similar effect on the distalization amount of maxillary first molars and the other dental changes.

### **Primary objective (s):**

Amount of maxillary fitst molar Distalization.

### Secondary objective:

Evaluate the other dental changes in the upper buccal segment accompanying the Distalization technique and dental changes in the incisors.

#### Study design

This research was a single-cantered, 2-arm parallel group randomized controlled clinical trial 1:1 allocation ratio, performed following the Consolidated Standards of Reporting Trials guidelines.

#### **Material and Methods**

### I) Participants, Interventions, and Outcomes

### A) Study Setting:

The study will be performed in the clinic of the Orthodontic Department at the Faculty of Oral and Dental Medicine, Future University in Egypt. The recruited sample would be from the Egyptian urban and rural population.

B) Eligibility: for the participants include the following:

(1) Adolescent patients aged 16-19 years.

(2) skeletal Class I ( $0^{\circ} < ANB < 4$ ).

(3) bilateral Class II molar relationship. defined by at least an end-to-end molar relationship.

(4) normal vertical growth pattern.

(5) full permanent dentition with unerupted upper third molars.

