Nur et al (2012), utilized the zygoma gear appliance to bilaterally distalize the maxillary molars and performed research to determine its dentoalveolar, skeletal, and soft tissue effects. The research group included fifteen patients (mean age, 15.87 1.09 years; range, 14–18 years), and lateral cephalometric images were obtained before and after distalization. A distalization force of 300 g per side was applied to the maxillary molars via the closed coil springs which replaced the heavy elastics in the previous design. The findings of the study showed that the maxillary molars were effectively distalized into a Class I relationship in all patients in a short time despite the presence of the maxillary second and third molars, the rate for the distal movement of the molars was 0.84 mm per month by total distalization of  $4.37 \pm 2.15$  mm without anchorage loss, while distal tipping measured only  $3.30^{\circ}$ ,maxillary first molars showed a slight intrusion (0.50 mm) and there were insignificant changes in both skeletal and soft tissue measurements.

Kilkis et al (2016), conducted a study to evaluate the dentoskeletal effects of the zygoma-gear appliance used for unilateral maxillary molar distalization, this study consisted of 21 patients with mean age  $15.68 \pm 2.18$  years and concluded that it was effective with significant amount of distalization for the maxillary first molar ( $5.31 \pm 2.46$  mm) in ( $0.45 \pm 0.12$  years), a 0.98 mm distalization rate per month

Aline Rode Santos et al (2017), conducted a tomographic study to evaluate the infra-zygomatic crest region thickness, in adult (male and female) patients. CBCT images from 40 patients were used to assess cross-sectional measurements of the infra-zygomatic crest region. Measurement 1 considered thickness 2 mm above the distobuccal root of the permanent maxillary first molar, while measurement 2 was taken 2 mm above the first measurement. The mean thickness of the infrazygomatic crest in males was 3.55 mm for measurement 1 and 2.84 mm for measurement 2, while in females these were 2.37 mm and 2.24 mm, respectively. The authors concluded that the overall mean thickness of the infrazygomatic crest was 2.49 mm with respect to measurement 1, and 2.29 mm for measurement 2, with no statistically significant differences between genders.

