### **o** Criteria of ending the distalization phase.

- Class I molar relation or at the end of pre-determined treatment duration (eight months).

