### **D]** Outcomes

### 1) Primary outcome

The primary outcome of the current study was to determine the total Anteroposterior position changes of upper first molars.

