### **Participant timeline:**

1. The principal investigator will screen the potential patients through careful clinical examination of patients at the orthodontic department, Faculty of Oral and Dental Medicine, Future University in Egypt.

2. All recruited patients should fulfil the previously mentioned inclusion and exclusion criteria.

3. Every participant will be asked to sign an informed consent before the beginning of the study.

4. After patient's enrolment, each participant will be asked for preintervention records to ensure proper diagnosis.

[figure not shown]
5. The principal investigator will randomly allocate the patients to one of the intervention groups.

**6.** After patient's enrolment, pre-intervention records will be taken for each participant to ensure proper diagnosis (T0).

7. Every 4 weeks Each patient will have follow up visit, for appliance activation, uptake of impression for interim records and checking for mini-screws stability (T1-T7).

**8.** Post- records for each participant will be taken after duration of eight months (T8) at the same visit of appliance removal.

[figure not shown]
**9.** The principal investigator will continue the normal orthodontic treatment and achieved proper finished occlusion for every patient after the end of the study.

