### **C] Statistical Analysis:**

• The principal investigator will be responsible for the extraction of the required data from the CBCT taken before and after retraction as well as the study models taken at every follow up visit. The data will be sent to a specialized statistician.

• The specialized statistician will be responsible for the statistical analysis of the study by:

- 1. Presenting the data as mean, standard deviation (SD) and Standard error (SE) values.
- 2. Using Paired t-test to compare between the friction and the frictionless group of retraction as well as to compare between the pre-and post -treatment data for each group.

3. Using Anova test to determine the rate of anterior segment retraction.

4. Statistically evaluate the patient acceptance for both techniques.

• For this study, the specialized statistician will use IBM11 SPSS12 Statistics Version 20 for Windows to perform the required statistics.

• The significance level will be  $P \le 0.05$ . Highly significant variables are detected when P value is less than 0.01.

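### The primary comparison of distance moved does not adjust for baseline Class II discrepancy, on which distance probably depends; the cost is precision, of uncertain size

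*Combined protocol and SAP*

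**What the plan says.** - **Entry** (B) Eligibility): "bilateral Class II molar relationship. defined by at least an end-to-end molar relationship". No upper limit and no millimetre value are given.
- **End of treatment** (Criteria of ending the distalization phase): "Class I molar relation or at the end of pre-determined treatment duration (eight months"). The text does not say which of the two takes precedence.
- **Final records** (Participant timeline, item 8): "Post- records for each participant will be taken after duration of eight months (T8) at the same visit of appliance removal". Nothing is said about a patient who reaches Class I sooner.
- **Primary outcome** (D] Outcomes): "The primary outcome of the current study was to determine the total Anteroposterior position changes of upper first molars", in millimetres. The monthly rate is a secondary outcome.
- **Allocation** (Sequence generation): random numbers from a spreadsheet, then sorted, 1:1. No stratification by severity is described.
- **Analysis** (Statistical Analysis): "Using Paired t-test to compare between the friction and the frictionless group of retraction as well as to compare between the pre-and post -treatment data". No baseline covariate is named, and the group labels belong to a different trial.

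**The concern.** A patient who stops on reaching Class I has moved roughly the distance that separated the molars from Class I at the start. Call that distance need. Entry admits any need from end-to-end upward, so need may vary a good deal between patients. To the extent that the Class I stop operates, this variation passes straight into the primary outcome.

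Need is fixed before randomisation and can be measured on pre-treatment models. With 11 patients per arm and unstratified allocation, the arms can differ in mean need by chance. An unadjusted comparison carries that difference as noise. At stake is the precision of the one comparison the trial is sized for.

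**Working it through.** **1. The plan's own figure.** Sample size calculation gives pilot means (SD) of 3.17 (0.81) and 4.32 (0.79) mm, three patients per group.
- Difference = 4.32 − 3.17 = 1.15 mm.
- Pooled SD = √((0.81² + 0.79²)/2) = 0.80 mm, so d = 1.15/0.80 = 1.437, as stated.
- A two-sided independent-samples t-test (noncentral t) has power 0.762 with 8 per group and 0.817 with 9. The plan's 9 per group reproduces; it is raised to 11 for dropout.
- That SD rests on 4 degrees of freedom; its 95% interval is 0.48 to 2.30 mm.

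**2. Would the Class I stop operate within eight months?** The literature review cites mean rates of 0.7, 0.84 and 0.98 mm/month.
- Eight months then allows 8 × 0.7 = 5.6 to 8 × 0.98 = 7.8 mm.
- The pilot distances would take 3.17/0.98 = 3.2 to 4.32/0.7 = 6.2 months.
- The cited 15-patient zygoma-gear study describes the teeth as "effectively distalized into a Class I relationship in all patients in a short time despite the presence of the maxillary second and third molars", after 4.37/0.84 = 5.2 months on average.
- If instead the pilot distances took all eight months, the rates were 3.17/8 = 0.40 and 4.32/8 = 0.54 mm/month, and the time limit would stop many patients first.

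So the stop could operate for most patients or for a minority.

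**3. Range of the dependence.** Simulation of distance = min(need, 8 × rate), assuming need with mean 4 mm, SD 1 mm and floor 2.5 mm, and rate SD 0.1 mm/month:

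| Rates (mm/month) | Reach Class I | Need–distance correlation | 8-month capacity difference → difference in distance |
|---|---|---|---|
| 0.40 vs 0.54 | 25%, 60% | 0.28, 0.74 | 1.15 → 0.67 mm |
| 0.70 vs 0.84 | 89%, 98% | 0.96, about 1.0 | 1.12 → 0.06 mm |

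**4. Chance imbalance in mean need.** SE = SD × √(2/11) = 0.43 SD. The SD of need is not given, so three assumed values are shown:
- 0.80 mm (pilot SD of distance): 0.34 mm, and 0.34/1.15 = 30%.
- 1.0 mm: 0.43 mm, 37%.
- 2.15 mm (SD of distance in the zygoma-gear study): 0.92 mm, 80%.

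An imbalance above 0.5 SD has a 24% chance. It reaches the outcome multiplied by the slope of distance on need, which is 1 if everyone stops at Class I and smaller otherwise.

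**5. What adjustment buys, by formula.** Residual SD = SD × √(1 − ρ²), with 2n − 3 degrees of freedom; ρ is assumed.
- SD 0.80 mm, 9 per arm: power 0.82 unadjusted; 0.81, 0.91 and 0.98 at ρ = 0, 0.5 and 0.7.
- SD 2.15 mm, 11 per arm, difference 1.15 mm: 0.22 unadjusted; 0.28, 0.39 and 0.78 at ρ = 0.5, 0.7 and 0.9.

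**6. What adjustment buys, by simulation** (same min(need, 8 × rate) model, 11 per arm). Need is uniform on 3–7 mm, or normal with SD 2.15 mm floored at 2 mm; both are assumptions, and figures are good to a point or two.
- 0.5 vs 0.8 mm/month, rate SD 0.15: power about 66% to 87% (uniform) and 31% to 64% (normal).
- 0.40 vs 0.54, uniform need: 76% to 78% at rate SD 0.10; 45% either way at rate SD 0.15 (SE 0.443 and 0.445 mm). With normal need and rate SD 0.10, 38% to 54%.
- 0.84 vs 0.98, normal need: the SE falls from 0.72 to 0.19 mm, but power stays near 5% because the difference itself has nearly vanished.

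**The case against.** The strongest reply is that dependence on need is inferred, not documented. The stopping rule has an eight-month alternative, and the timeline takes final records at eight months when the appliance comes off. If every appliance stays on until then, need does not cap distance. A reader might infer that treatment always runs to Class I, so that distance simply equals need. The documents do not support that, and they give no baseline need, no need–distance correlation and no expected share reaching Class I.

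A reader might also take 2.15 mm as the spread of need. It is the spread of distance moved in another study. The trial's own pilot SD is far smaller, though three patients per group make it weak evidence too.

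The largest simulated gain comes from chosen rates: 0.5 vs 0.8 mm/month implies an eight-month capacity difference of 2.4 mm, about twice the pilot difference. At slower rates the gain can disappear.

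Finally, chance imbalance is already reflected in the t-test's standard error, and simulated unadjusted type I error stayed at about 5%.

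All of this stands, and it limits the size of the point. It does not remove it. The omission is verifiable, the cited rates make some dependence likely, and adjusting costs next to nothing where the dependence is weak.

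**Conclusion.** The point holds as one about precision. Severity has a lower limit only, Class I is one of two ends of treatment, the outcome is total distance, and neither allocation nor analysis takes account of baseline discrepancy.

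The benefit of adjusting runs from nothing, where the time limit dominates, to between about 20 and just over 30 points of power at 0.5 vs 0.8 mm/month. The loss at zero correlation is about 0.01 in power. Where in that range this trial falls depends on the SD of need, the monthly rates and how the two eight-month passages are reconciled; none of these is settled in the documents.

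Two stronger conclusions might be drawn and are not supported. Leaving out the covariate does not bias the comparison, because allocation is random. And adjustment does not repair the outcome: where both arms stop at Class I, the true difference in distance is truncated and no covariate restores it.

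**What to change.** - In Statistical Analysis, define the primary comparison as an ANCOVA of total first-molar distance on arm plus T0 Class II discrepancy. Use one value per patient (mean of right and left), with the discrepancy in millimetres from Class I on the pre-treatment study models as the only covariate. This replaces the paired test between the mislabelled groups.
- Report T0 discrepancy by arm.
- Reconcile the criteria for ending distalization with item 8 of the Participant timeline, so that it is clear when the primary measurement is taken for a patient who reaches Class I before eight months.
- State that adjustment does not recover a difference truncated when both arms stop at Class I.

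Eligibility and treatment rules stay as they are.

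**Cost:** one measurement per side, one degree of freedom and a few sentences. The measurement needs upper and lower baseline models in occlusion. The plan mentions study models, impressions and scanning but no lower-arch scan or bite record, so their availability should be confirmed.

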# **Exclusion criteria included:**

- (1) a skeletal Class II or Class III relationship.
- (2) past orthodontic treatment.
- (4) poor oral hygiene.
- (5) Increased vertical dimension.

# C) Interventions:

# **O** Medical History Questionnaire:

will be filled by the patient to exclude the presence of any systemic condition.

# **O** Clinical Examination:

Proper examination of the oral structures including;

- Teeth will be examined for caries, fracture or missing teeth.
- Gingival tissues will be examined for gingivitis, periodontitis, attachment loss, gingival recession, oral lesions and the nature of the gingival biotype.
- Thorough intraoral examination is needed to evaluate the need for referral for consultation or intervention before the initiation of treatment.

### **O** Diagnosis

The patient is checked to fulfil the previously mentioned inclusion criteria. Full set of records will be taken for every patient (study models, lateral cephalometric radiographs, and photos as part of the routine procedure for treatment of patients in the outpatient clinic of the Orthodontic Department, future University in Egypt.

### **O** Clinical Procedure:

After taking pre-treatment records, every patient will receive:

- The third molars will be extracted surgically in the third molar extraction group four weeks before intervention commenced.
- Proper disinfection will be performed with a local disinfectant, BETADINE povidone-iodine 10%, at the area of mini-implant insertion.
- Two infra zygomatic mini-implants will be placed (Screw Tomas pin 10mm, dentaurum, Germany).
- Bands will be cemented to the upper first molars.
- The inner bow (1.2mm) is a modified version of the inner part of a conventional face bow. Two hooks were soldered onto the inner bow distal to the lateral incisor teeth regions. A U loop at the first premolar region and bends acting as a mesial stop will be bent in front of the maxillary first molars.

- The inner bow will be adjusted to the headgear tubes on the maxillary first molar bands, as the anterior component of the inner bow is 3 mm free from the labial surface of the anterior teeth.
- A distalization force of 300 gm/per side was applied to the maxillary molars via a closed coil spring (Tomascoil spring, Dentourum, Germany). According to the desired activation length, the distal end of the coil spring was set to the IZ mini-screw, while the mesial end was linked to the wire framework hook either directly or with a 0.01-inch stainless-steel ligature

